The study design is shown in Figure 4.a. Participants are expected to have data for Baseline (including CPP diagnosis and pre-ENANTONE treatment) phase, the ENANTONE treatment phase (at least 9 continuous months) and Follow-up phase (of variable duration depending upon the duration of available observations). During follow-up phase patients may have been treated with another GnRH after treatment with ENANTONE until discontinuing CPP therapy and allowed to progress to puberty or may have completed their treatment for CPP with ENANTONE and then progress to puberty.

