## **5.0 ANALYSIS OUTCOMES**

### **5.1 Primary Outcome**

1. Safety - Adverse events (AEs) and serious adverse events (SAEs) reported by physicians in the medical records (eg. incidence of any injection site reaction) during and after treatment with ENANTONE.
2. Effectiveness - Regression or no progression in Tanner staging during and after treatment with ENANTONE

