### **5.2 Secondary Outcome**

1. LH and FSH suppression to prepubertal level during and after treatment with ENANTONE
2. Estradiol or testosterone level suppression to prepubertal level during and after treatment with ENANTONE
3. Decrease in the ratio of bone age to chronological age (BA/CA ratio) during treatment with ENANTONE

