## **7.3 Disposition of Subjects**

The number and percentage of subjects, that complete ENANTONE therapy will be tabulated. Otherwise the reasons for not completing ENANTONE therapy will be tabulated. Subjects receiving other GnRHa therapies will be tabulated, and these other therapies will be tabulated, if possible.

The number and percentage of subjects as shown below will also be tabulated.

- Number of subjects
  - Total number of subjects in the ENANTONE treatment period
- Number and percentage of subjects in the follow-up phase after completing treatment with ENANTONE
  - Percentage who had been treated with only ENANTONE
  - Percentage who had been treated with ENANTONE in the treatment phase and then another GnRHa in the follow-up period
- Number and percentage of subjects who completed puberty in the follow-up phase

Puberty is defined as having a Tanner Stage = V after completion of GnRHa therapy with either ENANTONE only or ENANTONE followed by another GnRHa after ENANTONE

The following categories for the reason of primary discontinuation of ENANTONE therapy will be presented for this study.

- Lack of efficacy
- Adverse Event
- Change CPP therapy to another GnRH agonist
- Investigator Judgment
- Other

When the subject meets the protocol's eligibility criteria (inclusion criteria) and is henceforth enrolled into the study, the subject's missing data –if not satisfactory to fulfil a complete analysis for primary and secondary endpoints– will not be regarded as protocol deviation.

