### **7.8.1 Primary Efficacy Endpoint(s)**

The primary effectiveness outcome, percentage of subjects who have regression or no progression (i.e. response to treatment) in Tanner staging at the end of ENANTONE treatment (i.e. the last observation in the ENANTONE treatment phase) will be analyzed using an exact method. The 95% CI for the regression or no progression responder will be determined using Clopper-Pearson exact method. Similar analysis as described above will be performed at 3-month intervals from the initiation of ENANTONE treatment. Additional time intervals maybe utilized as fitting the data.

A Tanner Stage of 5 is satisfied when both evaluations for Tanner scoring are V; specifically, breast development and pubic hair for females and genital development and pubic hair for males.

Where applicable, similar summaries, using the appropriate baseline, will be presented for the follow-up phase at 3-month intervals.

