### **7.8.2 Secondary Efficacy Endpoint(s)**

The above analyses methodology and segmented summaries will be also applied to the following efficacy outcomes, at the end of the ENANTONE treatment and evaluated over time using the estimated study visits at 3-month intervals:

- Percentage of patients with peak LH suppression
- Percentage of patients with peak FSH suppression
- Percentage of patients with estradiol or testosterone level suppression to pre pubertal level
- Percentage of patients with a decrease from baseline in the ratio of bone age to chronological age only during treatment with ENANTONE

For each time point, a subject's peak LH (or FSH) value will be determined as largest value of the 0, 30, 60, 90 min samples from the stimulation test.

The abnormal values for a normal pediatric patient population in China for estradiol, testosterone, LH and FSH are listed in Table 2 below.

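### In off-treatment follow-up, the SAP's efficacy tables count expected puberty as non-response and continued suppression as success

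*SAP*

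**What the plan says.** **Outcomes.** SAP 5.1 gives the primary effectiveness outcome as "Regression or no progression in Tanner staging during and after treatment with ENANTONE". SAP 5.2 gives two of the secondary outcomes as "LH and FSH suppression to prepubertal level during and after treatment with ENANTONE" and "Estradiol or testosterone level suppression to prepubertal level during and after treatment with ENANTONE". Protocol 10.2.1 has the same time scope.

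**Analysis.** SAP 7.8.1 takes as its main measure the percentage with "regression or no progression (i.e. response to treatment) in Tanner staging at the end of ENANTONE treatment". For follow-up it says: "Where applicable, similar summaries, using the appropriate baseline, will be presented for the follow-up phase at 3-month intervals". SAP 7.8.2 opens with "The above analyses methodology and segmented summaries will be also applied to the following efficacy outcomes" and lists peak LH, peak FSH, estradiol or testosterone, and the bone age to chronological age ratio. Only the last is restricted to the ENANTONE period. Suppression is judged against fixed limits (Tables 2 and 3).

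**Segments and baseline.** SAP 7.1 and 7.8 split follow-up into ENANTONE-only subjects, time on another GnRHa, and time after that other GnRHa has ended. SAP 7.1.1 sets the follow-up baseline at the first value after the last dose of any GnRHa.

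**Expected course after stopping.** SAP 4.4 describes patients who may take another GnRHa "until discontinuing CPP therapy and allowed to progress to puberty", or who finish CPP treatment with ENANTONE and then enter puberty. SAP 7.3 tabulates the "Number and percentage of subjects who completed puberty in the follow-up phase", defined as Tanner stage V after GnRHa therapy.

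**The concern.** A responder definition should have the same favourable direction in every segment where it is used. While a child receives a GnRHa, holding Tanner stage and suppressing hormones are the aims of treatment. Once therapy has stopped, the SAP itself expects the opposite. Applied unchanged to off-treatment data, the definition makes an efficacy percentage fall as the planned course occurs and rise when it does not.

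Long-term effectiveness is Objective 2, and protocol 13.0 says the results go to the regulator to support long-term use. A follow-up efficacy table that declines every 3 months could be read as a waning effect when it shows puberty resuming as intended. A table that stays high could be read as lasting benefit when it shows children who have not resumed.

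**Working it through.** **The plan's own figure.** The documents give no planned or expected rate for follow-up. The only related figure is in protocol 10.5: margins of about 7% and 6% at effectiveness rates of 75% and 85%, with 300 subjects evenly split. It reproduces: 1.96 × √(0.75 × 0.25 / 150) = 6.93% and 1.96 × √(0.85 × 0.15 / 150) = 5.71%. It does not bear on the direction of the follow-up measure.

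**Step 1: what a follow-up Tanner percentage contains.** In an off-treatment segment and a given window, let N subjects have a follow-up baseline and a Tanner value, of whom k have progressed since that baseline. Then

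response = (N − k) / N = 1 − k/N.

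The N − k responders include two opposite groups: children who have not resumed puberty, and children already at Tanner V at the follow-up baseline, who cannot progress further.

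**Step 2: the same child in two tables.**

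| Off-treatment course | SAP 7.3 | SAP 7.8.1 |
|---|---|---|
| Below V at follow-up baseline, later reaches V | Completed puberty | Non-responder |
| Already at V at follow-up baseline | Completed puberty | No progression, so responder |
| Below V, no change | Not completed | Responder |

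**Step 3: hormones.** The limits do not vary by phase: estradiol 20 pg/mL; testosterone 7.34 nmol/L; peak LH 2.7 U/L (male) or 2 U/L (female); peak FSH 3.7 U/L (male) or 6.7 U/L (female). The suppression percentage is 1 minus the proportion above the limit. No baseline enters, so no choice of baseline changes its direction.

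**Step 4: does any wording correct this?** The follow-up baseline in SAP 7.1.1 does not, because resumed puberty is progression from it. The where-applicable clause in 7.8.1 names no segment to leave out. The explicit restriction on the bone age ratio shows that the authors limited an outcome to treatment where they meant to, and Tanner stage and hormones carry no such limit.

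**Step 5: arithmetic illustration.** The progression rates below are assumed. N = 100 is the SAP's total sample, so it is the most that could contribute. Intervals are Clopper-Pearson 95%.

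| Assumed progressed | Reported as response | Same data as progression |
|---|---|---|
| 25% | 75% (65.3 to 83.1) | 25% (16.9 to 34.7) |
| 50% | 50% (39.8 to 60.2) | 50% (39.8 to 60.2) |
| 75% | 25% (16.9 to 34.7) | 75% (65.3 to 83.1) |
| 90% | 10% (4.9 to 17.6) | 90% (82.4 to 95.1) |

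The table shows only the complement. It does not estimate what this study will find.

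**The case against.** The strongest reply is that little depends on these tables. SAP 7.8.1 ties the word response to the end of ENANTONE treatment. Protocol 10.7.3 likewise places the responder analyses at end of treatment and at yearly points from treatment start, with none in follow-up. Follow-up is reported separately, so resumed puberty cannot dilute the on-treatment rate. The summaries are descriptive, and SAP 7.13 has dropped the dose comparison. A reader shown the percentage without progression can subtract it from 100. SAP 7.10 also summarises hormones, menstruation, pelvic measurements and pregnancy by follow-up segment, so hormones that stay low off drug would be visible there.

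Most of this stands and limits the scope. It does not remove the point. The follow-up tables sit in the efficacy section and serve outcomes that SAP 5.1 and 5.2 extend past treatment. SAP 7.10 does not reverse the labels in 7.8, and its sexual-characteristic entry covers males only. Subtraction also cannot separate children already at Tanner V from those who have not resumed.

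Four stronger readings might be inferred and are not supported:

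- **The primary result is biased.** It is fixed at the last observation of the ENANTONE phase and is untouched.
- **All follow-up points the wrong way.** Time on another GnRHa does not; suppression is still the aim there.
- **Every completed-puberty subject is a non-responder.** This is true only of those who reach Tanner V after the follow-up baseline.
- **Follow-up response will approach zero, or persistent suppression is a safety signal.** The documents give neither a resumption rate or timing nor a statement that would support the second claim.

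**Conclusion.** The plan is wrong as written for off-treatment follow-up only. There, the 7.8.1 and 7.8.2 percentages run against the course that SAP 4.4 and 7.3 expect, and the Tanner percentage mixes completed puberty with puberty not resumed. This rests on reading the segmented summaries in 7.8.2 as including the follow-up segments of 7.8, which agrees with the outcome wording in 5.2. No size can be stated. It is worth correcting before the follow-up tables are produced, because it decides what those tables can be used to conclude.

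**What to change.** 1. In SAP 7.8.1 and 7.8.2, limit the Tanner responder and hormone suppression summaries to time on GnRHa: the ENANTONE phase and the other-GnRHa intervals.
2. For the two off-treatment segments, report with Clopper-Pearson intervals the percentage with Tanner progression from the follow-up baseline, showing subjects already at Tanner V separately. Report also the percentage with each hormone above its Table 2 upper limit. Label these as pubertal progression or recovery and place them with the long-term outcomes in 7.10.
3. Time from last dose to progression or recovery may be added descriptively. It should stay optional, because chart visits are irregular.
4. Record the change in SAP 7.13. Reconcile the time scope in SAP 5.1 and 5.2 and protocol 10.2.1, and also the protocol abstract, which limits estradiol or testosterone suppression to the treatment period.

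**Cost.** This is a documented departure from the stated outcome wording and a few re-specified tables. It uses the same data, with no new collection.

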10.0 RESEARCH METHODS

10.1 Study Design

10.1.1 Study Population and Design

This is an observational, retrospective study to evaluate long term safety and effectiveness of ENANTONE (leuprorelin acetate) in the treatment of CPP.

Approximately 300 patients with CPP, who were treated with ENANTONE for at least 9 continuous months, who initiated and received the last dose of treatment during the index period from 1 September 1998 to 30 September 2018, will be enrolled into the study. Patients who were treated with other GnRHa (including generic leuprorelin acetate) after the 9-months treatment with ENANTONE can be enrolled into the study. Within each site, sequential eligible patients will be enrolled until the site's patient quota has been reached. Medical records will be collected and reviewed.

[figure not shown]
Prior to ENANTONE treatment initiation, all relevant data (specified in Section 10.2.3.1), including data pertaining to the diagnosis of CPP will be collected at all available time points.

The **ENANTONE Treatment Phase** is the period during which patients were treated with at least 9 continuous months of ENANTONE. All relevant data (specified in Section 10.2.3.2) will be collected at all available time points.

The **Follow-up Phase** is the period after the ENANTONE Treatment Phase up to the day of last available follow-up data for the subject. All relevant data (specified in Section 10.2.3.2) will be collected at all available time points after the ENANTONE Treatment Phase. At a minimum, the data from the most recent time point available in the medical record should be included so as to include data on long term follow up of the subject. During the Follow-up Phase, a GnRHa Treatment Interval may apply to those patients who were treated with a GnRHa other than ENANTONE (either generic leuprorelin acetate or other GnRHa) for CPP; in this case, the dates of therapy with this other GnRHa should be noted in the case report form (CRF).

The study design is shown in [Figure 10.a](#).

Figure 10.a Overview of Study Design

(a) Baseline: First day of administration of ENANTONE.

(b) End of Follow-up: The day of last available follow-up data for the subject.

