10.2.2 Variables to be Collected

The following variables may be collected and recorded on the CRF as are available in the subject's chart. At a minimum, data related to the primary and secondary endpoints should be collected. This includes data at time of diagnosis of CPP, at the beginning of the ENANTONE Treatment Phase, at the end of the ENANTONE Treatment Phase and at the most recent time in the Follow-up Phase.

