10.7.3 Effectiveness Analysis

Any inferential statistical analysis resulting in p-values will be reported for the purpose of identifying notable findings rather than any formal test of statistical significance. Unless specified otherwise, all point estimates will be estimated alongside a companion 95% CI.

The primary effectiveness outcome, percentage of subjects who have regression or no progression (ie, response to treatment) in Tanner staging at the end of the ENANTONE Treatment Phase will be analyzed using a Cochran-Mantel-Haenszel (CMH) test with sex as

strata variable and dose (high, low) as independent variable. The adjusted odds ratio and 95% CI will be provided from the CMH test along with two-sided p-value. The 95% CI for the percent will also be determined using Clopper-Pearson exact method, unadjusted for sex, will be provided for overall responder and for each sub-response (regression/ no progression) for all subjects and by sex. If the final data are incompatible with the above analyses, then another method, such as ordinary percentages with 95% CIs (example using Wald type CIs), may be used.

Additional CMH analyses with adjustment by other demographic variables may be performed where necessary. If the data in the treatment period permits, similar analysis as described above will be performed at year intervals from the initiation of treatment, ie, Year 1, Year 2, etc.

The above analyses methodology will be also applied to the following effectiveness outcomes, at the end of the treatment phase and at year intervals, if appropriate:

- Percentage of patients with LH suppression
- Percentage of patients with FSH suppression
- Percentage of patients with estradiol or testosterone level suppression to prepubertal level
- Percentage of patients with a decrease from baseline in the ratio of bone age to chronological age
- Percentage of patients with an increase from baseline in predicted adult height

Change from baseline for BMI at end of treatment phase will be analyzed. This analysis will also be performed at each year interval, as permitted by available data and where applicable, of the treatment phase.

The above analysis will be used for the following quantitative variables, with associated baseline value as covariate:

- Change from baseline in BMI during the follow up phase, at yearly intervals, with end of treatment phase BMI as baseline
- Change from baseline in BMD, at end of treatment phase and at yearly intervals

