- Change from baseline in BMD during the follow up phase, at yearly intervals with the end of treatment phase bone density as baseline
- Change from baseline in patient height, at end of treatment phase and at yearly intervals
- Change from baseline in patient height during the follow up phase, at yearly intervals with end of treatment phase height as baseline

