### **7.8.3 Additional Efficacy Endpoint(s)**

Percent of patients with a change from baseline in the following parameters will be summarized in a similar manner as the above categorical secondary efficacy endpoint:

- Increase in predicted adult height during and after treatment with ENANTONE
- Change from baseline for BMI
- Change from baseline in BMD
- Change from baseline in patient height

For these and the other additional efficacy endpoints, descriptive statistics will be provided without inferential comparisons for the end of ENANTONE treatment phase and 3-month intervals and follow-up segments previously described.

- Increase in predicted adult height during and after treatment with ENANTONE
- Change from baseline in standard laboratory tests during and after treatment with ENANTONE
- Incidence rate of polycystic ovarian syndrome during and after treatment with ENANTONE
- Evaluation of long term effect on reproduction
- Change from baseline for BMI

- Change from baseline in BMD
- Change from baseline in patient height

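### For follow-up BMI, BMD and height, the SAP replaces the protocol's yearly intervals and end-of-treatment baseline with 3-month windows and a post-treatment baseline, does not list either change, and names no pooled last-follow-up summary.

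*SAP*

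**What the plan says.** **Protocol, follow-up.** Section 10.7.3 plans "Change from baseline in BMI during the follow up phase, at yearly intervals, with end of treatment phase BMI as baseline" and "Change from baseline in patient height during the follow up phase, at yearly intervals with end of treatment phase height as baseline". BMD has the same interval and the same kind of baseline.

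**Protocol, Tanner stage.** The yearly repeat in 10.7.3 concerns the treatment period: "If the data in the treatment period permits, similar analysis as described above will be performed at year intervals from the initiation of treatment". No follow-up interval is set for Tanner stage.

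**Protocol, minimum follow-up data.** Section 10.1.1 says "At a minimum, the data from the most recent time point available in the medical record should be included", so that long-term data are captured. SAP 4.4 repeats this. Protocol 10.2.2 asks for primary and secondary endpoint data "at the end of the ENANTONE Treatment Phase and at the most recent time in the Follow-up Phase".

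**SAP, intervals.** Section 7.8.1 says of Tanner stage that, where applicable, "similar summaries, using the appropriate baseline, will be presented for the follow-up phase at 3-month intervals". Section 7.8.3 gives descriptive statistics for BMI, BMD and height "for the end of ENANTONE treatment phase and 3-month intervals and follow-up segments previously described". Section 7.1.3 applies the Table 1 windows to both periods and extends them as far as the data go. Section 7.1.2 counts days from the first ENANTONE dose and gives no separate origin for follow-up.

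**SAP, baseline.** Under 7.1.1 the follow-up baseline is the first available measurement after the last dose of any GnRHa.

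**SAP, size and changes.** Section 6.0 reduces the sample from 300 to 100. Section 7.13 reports only that the dose comparison and the CMH test are dropped.

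**The concern.** Objective 2 is long-term effectiveness, and the sample is a third of the size first planned. For BMI, BMD and height the SAP nevertheless divides follow-up four times as finely as the protocol, and 7.8 splits results further by sex and by GnRHa segment. It also moves the baseline from the end of treatment to a later point. A child with one late measurement has no change from that later baseline, although the record is there and the protocol's baseline could use it.

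The most recent record is the follow-up time point the documents single out, yet no summary is defined at it. The treatment phase does have such a summary, at its last observation. A reader of SAP 7.13 would not learn that the interval and the baseline had changed.

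**Working it through.** **1. The plan's own precision figures.** Protocol 10.5 states margins of about 7% and 6% at rates of 75% and 85%, with 300 children split evenly.
- Half-width = 1.96 × √(p(1−p)/n). With n = 150: 1.96 × √(0.75 × 0.25/150) = 6.9%, and 1.96 × √(0.85 × 0.15/150) = 5.7%.
- Odds ratio = (0.85/0.15)/(0.75/0.25) = 1.89. The standard error of its log is √(1/127.5 + 1/22.5 + 1/112.5 + 1/37.5) = 0.296, so the 95% CI is 1.06 to 3.38.

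Both figures reproduce. They concern the primary effectiveness rate at N = 300. With 100 children split evenly the margins become 12.0% and 9.9%. Neither document gives a precision figure for follow-up.

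**2. The two plans for follow-up BMI, BMD and height.**

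| | Protocol 10.7.3 | SAP 7.1.1, 7.1.3, 7.8.3 |
|---|---|---|
| Interval | yearly | 3 months |
| Baseline | end of treatment phase | first value after last GnRHa dose |
| Listed in SAP 7.13 | – | no |

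**3. Effect of the baseline.** Suppose a child has k measurements after the last GnRHa dose.
- Under the SAP the first of them is the baseline, which leaves k − 1 change values. With k = 1 there are none.
- Under the protocol the same measurements give up to k change values, provided an end-of-treatment value exists.
- The SAP's treatment phase runs to 45 days after the last dose. A measurement in that tail can serve as the follow-up baseline, so a child with one value there and one later does contribute.

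**4. Effect of the interval.** The documents give no number of children with follow-up data, no follow-up length and no visit frequency. Assume one record per child, N children, spread evenly over F years. Records per 3-month window = N/(4F); per yearly window = N/F.

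| N | F (years) | per 3-month window | per yearly window |
|---|---|---|---|
| 100 | 2 | 12.5 | 50 |
| 100 | 5 | 5 | 20 |
| 100 | 10 | 2.5 | 10 |
| 60 | 2 | 7.5 | 30 |
| 60 | 5 | 3 | 12 |
| 60 | 10 | 1.5 | 6 |

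These are counts of records. In this one-record case the SAP baseline yields no change values at all (step 3), so the precision below presumes a usable baseline.

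**5. What those counts mean for precision** (N = 100, F = 5, before any split by sex or segment).
- Mean change: half-width = t(0.975, n−1)/√n, in units of the SD of the change. For n = 5: 2.776/√5 = 1.24 SD. For n = 20: 2.093/√20 = 0.47 SD. For all 100 last records: 1.984/√100 = 0.20 SD.
- A proportion near 75%, Clopper-Pearson: 4/5 gives 28% to 99.5%; 15/20 gives 51% to 91%; 75/100 gives 65% to 83%. With 60 children pooled, 45/60 gives 62% to 85%.

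If children were instead seen about every 3 months, each would appear in many windows. Early windows could then hold most of those still in follow-up, and the loss would be much smaller.

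**The case against.** The strongest reply is that follow-up is neither ignored nor closed to other summaries. Windows extend to reach any record (SAP 7.1.3), and individual data are listed (7.8). Completion of puberty in follow-up is one percentage outside any window (7.3). Reproductive outcomes are summarised by follow-up segment (7.10). The mention of follow-up segments in 7.8.3 can be read as including whole-segment summaries, and 7.8.1 adds "Additional time intervals maybe utilized as fitting the data". All of this stands, so it would be wrong to infer that follow-up data are never summarised. The latitude in 7.8.1 sits beside the treatment-phase analysis, however, and specifies nothing. Intervals chosen once the data are seen do not replace a stated plan.

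A reader might also infer that the SAP overrode a yearly follow-up rule for Tanner stage. It did not, because the protocol sets none. Nor is a last follow-up record guaranteed. The wording is that it should be included. It is not an inclusion criterion (Protocol 10.4.1), missing data are not a deviation (10.2.3), and the minimum in 10.2.2 covers primary and secondary endpoints, not BMI, BMD or height.

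Finally, both documents collect follow-up at all available time points, so one record per child is an assumption and windows of two or three children are not a fact. That is correct, and the working shows the range for this reason.

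Comparing measured height at completed puberty with baseline predicted height may look like a natural addition. It would be a new endpoint found in neither document. Prediction methods may vary between children (Protocol 10.2.2.6), and statisticians could differ on it. It is no part of this point.

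**Conclusion.** The point holds for follow-up BMI, BMD and height. The SAP departs from the protocol in both interval and baseline and does not list either change in 7.13. Children with a single measurement after the last GnRHa dose drop out of the follow-up change analysis. That part follows from the definitions and needs no assumption; how many children it affects is unknown. No pooled estimate at the most recent follow-up record is specified for these variables or for Tanner stage.

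The cost in precision is conditional. Under one record per child, 3-month windows hold a quarter of the records of yearly ones: about 1.5 to 12.5 against 6 to 50 over the assumed range. With frequent visits the difference is much smaller.

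It would go too far to conclude that long-term effectiveness gets no usable estimate. The primary responder rate at the end of treatment is pooled with an exact CI, and inclusion requires the Tanner record it needs. This is a low-cost improvement to the follow-up summaries of a descriptive study, and the end-of-treatment result is not affected.

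**What to change.** - **SAP 7.1.1:** for follow-up BMI, BMD and height, use the end-of-treatment value as baseline, as in Protocol 10.7.3.
- **SAP 7.1.3:** use yearly windows in follow-up for these variables and state the day from which follow-up windows are counted. Keep the 3-month windows for the treatment phase.
- **SAP 7.8.3:** add a row for last available follow-up for BMI, BMD and height, with n, 95% CI, age and time since last GnRHa. Add the same row, descriptively, for Tanner stage in 7.8.1.
- **SAP 7.13:** list the departures from the protocol that remain, and the added row.

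The cost is SAP wording and a few tables, with no new data. Follow-up timing becomes coarser. The last-record row pools children at different times since therapy, which is why age and time since last GnRHa should stand beside it. Children without an end-of-treatment value for a variable will still have no change value, so n must be shown in each row.
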